## 9 STATISTICAL ANALYSIS PLAN

The statistical analysis of the data obtained from this study will be conducted by the Experimental Medicine Statistics Department in collaboration with the Translational Medicine Departments of the Sponsor. If, after the study has begun, changes are made to the statistical analysis plan stated below, then these deviations to the plan will be listed, along with an explanation as to why they occurred, in the Results Memo for this study.

### 9.1 Statistical Analysis Plan Summary

This section contains a brief summary of the statistical analyses for this study. Full detail is in the Statistical Methods (Section 9.6).

To assess the primary hypothesis, the repeated measurements associated with proportion of correct response in the OCL task at each of Weeks -1, 2, 4, 6 and 8 will be averaged by each participant. Intermittent missing repeated measures within a time point (e.g., Week 2) will not be imputed and data will be averaged as available. Observations with integrity failures will be excluded from analysis and will not be imputed. Change from placebo run-in period (i.e. Week -1) in the average correct response of OCL measurements will be estimated using a linear mixed effects model containing fixed effects for Week, proportion of correct response in the OCL measurement at baseline (placebo run-in period), Treatment (donepezil/placebo) and Week by Treatment interaction with an unstructured covariance matrix which will account for missing data under a missing at random assumption. Least square variances will be estimated for change from placebo run-in period by treatment group (donepezil/placebo) and Week 8 using above mentioned linear mixed models. The posterior distribution of the variances will be estimated by generating 10,000 independent draws from non-informative Inverse Gamma prior for both treatment groups. Conditioned on each variance, difference of average correct response rate of OCL task from placebo run-in period will be generated from a Normal distribution with mean equal to the estimated least square mean estimate for both groups at Week 8. The posterior probability of true mean difference between donepezil and placebo group at Week 8 relative to Week -1 is greater than 2 percentage points will be derived from the posterior distribution. A posterior probability that is > 55% will satisfy the primary hypothesis.

Power: The probability to satisfy the primary hypothesis under varying true mean change in donepezil population is shown in Table 9. With 36 participants (24 in donepezil and 12 in placebo), there is ~ 64% power to satisfy the criteria (posterior probability >55%) for the primary hypothesis if the true mean change from placebo run-in period is 3 percent points for donepezil group, assuming there no change in placebo group. For the donepezil group, if the true mean change is 4 percentage points then the corresponding power increases to 78%.

Table 9 Power Primary Hypothesis

| True Mean Change in Donepezil | Prob (Post prob. of difference of true mean change from placebo run-in between the donepezil and placebo groups > 0.02) > |         |         |
|-------------------------------|---|---------|---------|
|                               | P = 60%   | P = 55% | P = 50% |
| 2.0%                          | 0.407   | 0.456   | 0.509   |
| 2.5%                          | 0.483   | 0.532   | 0.582   |
| 3.0%                          | 0.576   | 0.635   | 0.684   |
| 3.5%                          | 0.669   | 0.713   | 0.754   |
| 4.0%                          | 0.741   | 0.778   | 0.816   |

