## 4 STUDY DESIGN

### 4.1 Overall Design

This is a randomized, placebo-controlled, parallel-group, multi-site study to evaluate the effects of donepezil 10 mg PO daily on cognitive function using a high-frequency site-based computerized cognitive assessment, the Cogstate Computerized Battery, in participants with MCI or mild AD.

The study will enroll approximately 36 participants randomized to receive over-encapsulated donepezil or placebo in a 2:1 ratio following a single blinded run-in period with placebo. No formal stratification is planned per site; however, an allocation schedule with separate panels for disease status (ie, Panel A for MCI and Panel B for mild AD) will be used with each panel incorporating randomization in a 2:1 ratio. Efforts will be made to enroll a minimum of 12 participants meeting AD diagnostic criteria (Panel B) in this study. The number of participants per panel (ie, disease status) may be adjusted by the Sponsor based on

enrollment metrics to ensure timely study completion, but the total sample size of the study will remain at approximately 36. The rationale for ensuring this minimum number of participants meeting AD criteria is that prior data suggest a more robust treatment signal for OCL testing in this population, and ensuring adequate representation of mild AD in the overall study sample will increase probability of study success.

Potential participants will have a Screening Visit (V1) to determine if they meet inclusion and exclusion criteria. Following the Screening Visit, participants will have a Baseline/Familiarization Visit (V2), during which the Cogstate battery will be administered for familiarization purposes as described in Section 1.3 (SoA). Participants who met the selection criteria at that point will return for 2 additional visits (V3 and V4) during that week, when a Cogstate battery as described in Section 1.3 (SoA) will be administered to further acclimate them to the high-frequency testing paradigm, and to provide a standard replicate testing period consistent with a mock baseline assessment initiating the placebo run-in period. As part of the testing during this week, participants will also undergo additional paper/pencil cognitive baseline (pre-treatment) assessment for the purposes of characterization of baseline cognitive status across several different performance domains before randomization into one of two treatment sequences.

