### **Baseline/Familiarization Visit and Testing Period 1 (Visits 2-4)**

At least 2 weeks following Screening Visit 1, participants who have met the selection criteria thus far, will return to the CRU to undergo procedures to confirm eligibility at the Baseline/Familiarization Visit (Visit 2). This will be the first of 3 cognitive testing days for the first testing period in this study. This first testing period is to familiarize the participants with the Cogstate battery as well as the high frequency testing schedule, and to ensure potential participants are able to complete the computerized cognitive assessments.

At this visit, the CBB (which consists of the DET, IDN, OCL, ONB subtests) will be administered 2 times separated by a rest period of approximately 15 minutes.

During this first testing period and throughout the study, participants will report to the CRU at approximately the same time in the morning (+/- 2 hours) for each testing visit. Cogstate assessments should be performed before any other procedures planned for a study visit (See Section 1.3 for a list of procedures). See Table 6 in Section 8.10.2 for recommended timings with built-in testing breaks on the longer testing visits.

Participants who have met all selection criteria at Randomization Visit 4 will be assigned randomization numbers and dispensed medication to take home, with instructions to take the first dose later that evening before retiring for bed. Study intervention dosing diary will be given to the participant with instructions to record dosing information nightly.

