## 9.4 Analysis Endpoints

Primary Endpoint:

Proportion of correct responses in the One Card Learning (OCL) task (a task of visual learning) at Weeks -1, 2, 4, 6 and 8.

Exploratory Endpoints:

- Other measures of Cogstate test battery (Detection (DET), Identification (IDN), One Back (ONB), International Shopping List Test (ISLT), Modified Groton Maze Learning Test (GMLTM), Continuous Paired Associate Learning (CPAL), International Daily Symbol Substitution Test -Medicines (IDSSTM), International Shopping List Test - Delayed Recall (ISRL)) at Weeks -1, 2, 4, 6 and 8.
- Measures related to the Face-Name Associative Memory Exam (FNAME).
- Measures related to Free and Cued Selective Reminding Test at Weeks -3 and 8.
- Measures related to Wechsler Adult Intelligence Scale (WAIS-IV) Coding at Weeks -3 and 8.
- Measures related of D-KEFS (Sorting, Verbal Fluency, Category Fluency, Twenty Questions) at Weeks -3 and 8.
- Measures related to beta-amyloid and phosphor-tau proteins.
- Measures related to PK data.
- Measures that capture the concept of operational feasibility of frequent site-based administration of cognitive function testing in participants with MCI/mild AD.
- Measures participants' and study partner/informants' perception and comfort with the use of at-home device (e.g. tablet/computer) in future studies.

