## 9.6 Statistical Methods

The primary hypothesis is related to proportion of correct response in the OCL task associated with change from placebo run-in period (Week -1) at Week 8 for donepezil group compared with placebo group. To assess the primary hypothesis, the repeated measurements

associated with proportion of correct response in the OCL task at each of Weeks -1, 2, 4, 6 and 8 will be averaged by each participant. Intermittent missing repeated measures within a time point (e.g., Week 2) will not be imputed and data will be averaged as available. Observations with integrity failures will be excluded from analysis and will not be imputed. The amount and patterns of missing data will be summarized. Change from placebo run-in period in the average correct response of OCL measurements will be estimated using a linear mixed effects model containing fixed effects for Week, proportion of correct response in the OCL measurement at baseline (placebo run-in period), Treatment (donepezil/placebo) and Week by Treatment interaction with an unstructured covariance matrix which will account for missing data under a missing at random assumption. Least square variances will be estimated for change from placebo run-in period by treatment group (donepezil/placebo) and Week 8 using above mentioned linear mixed models. The posterior distribution of the variances will be estimated by generating 10,000 independent draws from non-informative Inverse Gamma prior for both treatment groups. Conditioned on each variance, difference of average correct response rate of OCL task from placebo run-in period will be generated from a Normal distribution with mean equal to the estimated least square mean estimate for both groups at Week 8. The posterior probability of true mean difference between donepezil and placebo group at Week 8 relative to Week -1 is greater than 2 percentage points will be derived from the posterior distribution. We can rewrite the model as following

$$\sigma^2 \sim \text{Inverse Gamma}(\alpha, \beta), \text{ where } \alpha = \beta = 0.0001$$
$$\sigma_{trt}^2 | y_{iw} \propto \text{Inverse Gamma} \left( \alpha + \frac{n_{trt}}{2}, \beta + \frac{n_{trt}}{2} S_{trt}^2 \right), \text{ where } trt = \text{donepezil, placebo}$$
$$y_i | \cdot \sim \text{Normal}(\hat{\mu}_{trt}, \sigma_{trt}^2 | \cdot), \text{ where } i = \begin{cases} 1, \dots, 24 & \text{when } trt = \text{donepezil} \\ 1, \dots, 12 & \text{when } trt = \text{placebo} \end{cases}$$

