## 9.9 Sample Size and Power Calculations

The probability to satisfy the primary hypothesis under varying true mean change in donepezil population is shown in [Table 10](#). There are 24 participants in the donepezil group and 12 participants in the placebo group. In the placebo group, true mean change from placebo run-in period is assumed to be zero with SD of 0.06. In the donepezil group, the SD of the change from placebo run-in is 0.07. SD in both groups are consistent with estimated SD from MK-0000-318 study. With 36 participants (24 in donepezil and 12 in placebo), there is  $\sim 64\%$  power to satisfy the primary hypothesis if the true mean change from placebo run-in period is 3 percentage points for donepezil group, assuming there no change in placebo group. For donepezil group, if the true mean change is 4 percentage points then the corresponding power increases to 78% as displayed in the last row of [Table 10](#).

Table 10 Power associated with Primary Hypothesis

| True Mean Change in Donepezil | Prob (Post prob. of difference of true mean change from placebo run-in between the donepezil and placebo groups > 0.02) > |         |         |
|-------------------------------|---|---------|---------|
|                               | P = 60%   | P = 55% | P = 50% |
| 2.0%                          | 0.407   | 0.456   | 0.509   |
| 2.5%                          | 0.483   | 0.532   | 0.582   |
| 3.0%                          | 0.576   | 0.635   | 0.684   |
| 3.5%                          | 0.669   | 0.713   | 0.754   |
| 4.0%                          | 0.741   | 0.778   | 0.816   |

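### Should the primary model also adjust for the OCL scores collected at Visits 2-4, before randomisation?

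*Combined protocol and SAP*

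**What the plan says.** SAP Section 9.6 models change from the placebo run-in with fixed effects for Week, "proportion of correct response in the OCL measurement at baseline (placebo run-in period), Treatment (donepezil/placebo) and Week by Treatment interaction", and an unstructured covariance matrix. Section 9.1 gives the same model, with the "proportion of correct response in the OCL measurement at baseline (placebo run-in period") as covariate. The only OCL covariate is therefore the Week -1 mean, from Visits 5-7.

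Section 9.4 lists the primary endpoint as "Proportion of correct responses in the One Card Learning (OCL) task (a task of visual learning) at Weeks -1, 2, 4, 6 and 8". Week -3 is absent for OCL, although the same section uses it for the paper-and-pencil tests, for example "Measures related to Free and Cued Selective Reminding Test at Weeks -3 and 8".

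The Schedule of Activities (Section 1.3) places the Cogstate Brief Battery, which contains OCL, at Visits 2, 3 and 4, with two runs at Visit 2. Randomisation comes at the end of Visit 4. The protocol gives this period two roles. Section 4.1 says it serves to acclimate participants and "to provide a standard replicate testing period consistent with a mock baseline assessment initiating the placebo run-in period". Section 8.10.1 says "This first testing period is to familiarize the participants with the Cogstate battery as well as the high frequency testing schedule" and to check that they can complete the tests. Inclusion criterion 16 and its note use Cogstate performance at these visits for eligibility and for queries before randomisation.

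**The concern.** Four OCL scores per participant exist before any treatment is assigned, and the primary model ignores them. A covariate measured before randomisation cannot bias the treatment comparison, and adding one would leave change from Week -1 as the response. The trial is small, and Section 9.9 gives only about a 64% chance of meeting the primary criterion at a true 3-point change. Better precision would raise that chance with no extra visits. The protocol's own term for the period invites its use as a second baseline, and the SAP does not say why OCL at Week -3 was left out when the paper-and-pencil tests at Week -3 were kept. What is at stake is efficiency only; the planned comparison is not biased.

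**Working it through.** **Inputs.** From Section 9.9: 24 donepezil and 12 placebo participants; "In the donepezil group, the SD of the change from placebo run-in is 0.07"; placebo SD 0.06 with mean change zero. From Section 9.6: success requires a posterior probability above 55% that the difference exceeds 0.02. The documents give no correlation between testing periods, so those values are assumptions shown over a range.

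**Reproducing the plan's power.**

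SE = √(0.07²/24 + 0.06²/12) = √(0.000204 + 0.000300) = 0.02245.

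Power = Φ((d − 0.02)/SE − 0.1257), where 0.1257 is the normal quantile for 55%.

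- d = 0.03: Φ(0.4454 − 0.1257) = 62.5% (Table 10: 63.5%).
- d = 0.04: Φ(0.8907 − 0.1257) = 77.8% (Table 10: 77.8%).

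A simulation of the SAP's inverse-gamma rule gave 62.2% and 77.6%.

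**Effect of a second covariate.** Let r be the correlation of Week -1 with Week 8, and also of Week -3 with Week -1. Let k·r be the correlation of Week -3 with Week 8. The partial correlation of Week -3 with Week 8, given Week -1, is

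p = r(k − r)/(1 − r²).

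The SE is multiplied by f = √((1 − p²) × 32/31), where 32/31 is the cost of going from one covariate to two with 36 participants.

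Example with r = 0.5, k = 1: p = 0.5 × 0.5/0.75 = 0.333; f = √(0.889 × 1.032) = 0.958; power at 3 points = Φ(0.01/(0.02245 × 0.958) − 0.1257) = 63.3%.

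| k | r | p | f | Power change at 3 points | at 4 points |
|---|---|---|---|---|---|
| 1.0 | 0.3 | 0.231 | 0.989 | +0.19 | +0.31 |
| 1.0 | 0.5 | 0.333 | 0.958 | +0.74 | +1.15 |
| 1.0 | 0.8 | 0.444 | 0.910 | +1.65 | +2.53 |
| 0.9 | 0.5 | 0.267 | 0.979 | +0.36 | +0.56 |
| 0.9 | 0.7 | 0.275 | 0.977 | +0.40 | +0.62 |
| 0.8 | 0.5 | 0.200 | 0.995 | +0.08 | +0.12 |
| 0.8 | 0.7 | 0.137 | 1.006 | −0.11 | −0.17 |
| 0.7 | 0.5 | 0.133 | 1.007 | −0.12 | −0.18 |
| 0.7 | 0.7 | 0 | 1.016 | −0.27 | −0.42 |

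Power changes are in percentage points.

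**Break-even.** f = 1 when p² = 1 − 31/32 = 0.03125, so p = 0.177. Solving for k gives k = (0.177(1 − r²) + r²)/r, which is 0.77, 0.79, 0.83 and 0.88 for r = 0.5, 0.6, 0.7 and 0.8. Week -3 must keep roughly 77% to 88% of Week -1's correlation with Week 8 before the covariate pays for itself.

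**Decay with time.** Under a first-order autoregressive pattern, Week -3 carries no information about Week 8 beyond Week -1, so p = 0. Simulated analyses of covariance (20,000 trials per setting) gave a variance ratio of 1.03 to 1.04, a small loss. Under equal correlations of 0.5, 0.7 and 0.8 they gave 0.92, 0.86 and 0.83, in line with f² from the formula.

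**Reading of the SDs.** Those in Section 9.9 are for unadjusted change. If both models are credited with their adjustment under equal correlation, power at 3 points goes from 64.8% to 65.7% (r = 0.5) or from 63.2% to 64.9% (r = 0.8). The size of the gain is the same.

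**The case for a change.** The best case for acting rests on the protocol's own argument. Section 4.2 holds that more frequent testing locates a participant's true baseline better, yet the model adjusts for three Week -1 tests and leaves out four earlier ones. Familiarisation is a reason not to measure change from Visits 2-4, but it does not disqualify them as a covariate: a practice shift shared by everyone leaves correlations intact, and Section 4.2.1.4 claims that these tests lack learning effects. In the favourable case (r = 0.5 to 0.7) the variance ratios of 0.918 and 0.857 are worth about 3 to 6 participants (36/0.918 = 39.2; 36/0.857 = 42.0). Section 4.2 also records that the predecessor study took 26 months to complete.

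Much of this stands. The data are free, the adjustment would be unbiased, and the SAP gives no reason for the omission. It does not show a gain, however. Learning that differs between participants would weaken the correlation, and two of the four scores come from the day of first exposure. Week -3 is also further from Week 8 than Week -1 is. The change would need further choices as well: which visits to average, and how the adjusted variance enters the arm-specific variances of Section 9.6. If made after the study has begun, it would fall under the Section 9 rule that "these deviations to the plan will be listed, along with an explanation as to why they occurred, in the Results Memo". That is a modest burden, but the return could be negative.

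**Conclusion.** No change is needed. The observation is correct: the Week -1 mean is the only OCL covariate, and no listed analysis uses the Visits 2-4 scores. Those visits still do the work the protocol gives them, namely familiarisation and eligibility or performance checks. The planned model is valid, and the stated power takes no explicit credit for baseline adjustment, so the omission makes no figure wrong.

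The possible effect runs from a loss of about 0.3 to 0.4 percentage points of power to a gain of about 1.7 (3-point change) or 2.5 (4-point change). The gain at 3 points falls to 0.4 or less once Week -3 predicts Week 8 10% less well than Week -1 does. For scale, the normal approximation and Table 10 already differ by 1.0 point at the 3-point change. Experienced statisticians could reasonably choose either model.

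This rests on assumed correlations, on a single-time-point analysis of covariance standing in for the repeated-measures model, and on the SDs in Section 9.9. Correlations from MK-0000-318, which the documents do not report, could show whether the partial correlation exceeds 0.18. Without them, keeping one baseline covariate in a 36-participant trial is a sound choice.

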## 9.2 Responsibility for Analyses

The statistical analysis of the data obtained from this study will be the responsibility of the Experimental Medicine Statistics department of the Sponsor.

## 9.3 Hypotheses/Estimation

Primary:

After 8 weeks of daily treatment, the change from placebo run-in period (Week -1) in average proportion of correct responses in the One Card Learning (OCL) task (a task of visual learning) in participants receiving donepezil compared with participants receiving placebo will be  $\geq 2$  percentage points.

Secondary:

- The overall standard deviation associated with the change from placebo run-in period in average OCL repeated measurements (arcsine square root transformed) after 8 weeks of donepezil treatment is  $\leq 0.1$ .
- After 8 weeks of daily treatment in subjects receiving donepezil, the proportion of correct responses in the OCL task will improve relative to performance on the placebo run-in period by a clinically meaningful (>2 percentage points) degree of change.

## 9.4 Analysis Endpoints

Primary Endpoint:

Proportion of correct responses in the One Card Learning (OCL) task (a task of visual learning) at Weeks -1, 2, 4, 6 and 8.

Exploratory Endpoints:

- Other measures of Cogstate test battery (Detection (DET), Identification (IDN), One Back (ONB), International Shopping List Test (ISLT), Modified Groton Maze Learning Test (GMLTM), Continuous Paired Associate Learning (CPAL), International Daily Symbol Substitution Test -Medicines (IDSSTM), International Shopping List Test - Delayed Recall (ISRL)) at Weeks -1, 2, 4, 6 and 8.
- Measures related to the Face-Name Associative Memory Exam (FNAME).
- Measures related to Free and Cued Selective Reminding Test at Weeks -3 and 8.
- Measures related to Wechsler Adult Intelligence Scale (WAIS-IV) Coding at Weeks -3 and 8.
- Measures related of D-KEFS (Sorting, Verbal Fluency, Category Fluency, Twenty Questions) at Weeks -3 and 8.
- Measures related to beta-amyloid and phosphor-tau proteins.
- Measures related to PK data.
- Measures that capture the concept of operational feasibility of frequent site-based administration of cognitive function testing in participants with MCI/mild AD.
- Measures participants' and study partner/informants' perception and comfort with the use of at-home device (e.g. tablet/computer) in future studies.

## 9.5 Analysis Populations

The Full Analysis Set for each endpoint will be comprised of all participants who receive study medication and yield at least one valid measurement for that endpoint. Data from participants who discontinue donepezil therapy will be considered missing at time points after therapy discontinuation.

